11.3 Statistical Analysis

The primary efficacy analysis will include all patients to be analyzed and will be performed according to the ITT principle. Primary analysis provides confirmatory statistical evidence. Further analyses will be regarded exploratory (hypothesis generating) and will be interpreted accordingly.

The primary endpoint, the OR rate 6 months after end of treatment, will be tested using one-sample binomial test for the non-inferiority hypothesis. The respective null hypothesis is $H_0: p \leq p_0 - \delta = 0.95 - 0.1 = 0.85$,

where p is the ORR of the interventional 20Gy treatment, $p_0=0.95$ is the assumed ORR of the standard 30Gy treatment based on historical data, and $\delta=0.1$ is the non-inferiority margin.

Beyond the ITT analysis of the primary outcome, sensitivity analyses will be performed. In per-protocol analyses only patients without major protocol violations are included.

Statistical analyses of the pre-specified secondary endpoints will be performed using descriptive and inductive statistical methods according to the type of variable.

Additional exploratory analyses will include model-based analyses, subgroup analyses, and safety analyses. In safety analyses all study patients that underwent radiation therapy will be included (safety population).

12 Data Sources and Data Management

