Inclusion Criteria:	
 -primary indolent gastric or duodenal lymphoma -pathology: marginal zone lymphoma (MZL) or follicular lymphoma (FL) -stage: clinical stage I or II (Ann Arbor classification) -H. pylori negative or antibiotic resistant lymphoma -any FLIPI score low – high (0-4) -any size of tumor or affected lymph nodes -male or female with age \geq 18 years -performance status ECOG 0 – 3 -written informed consent by the patient
Exclusion Criteria:	
 -prior radiation treatment of the gastrointestinal lymphoma -stage: clinical stage III or IV (Ann Arbor classification)-inability to understand the informed consent or unwillingness to participate in the study -severe comorbidity or organ dysfunction contraindicating the use of RT (liver cirrhosis Child-Pugh C, chronic obstructive pulmonary disease GOLD 4, heart insufficiency NYHA IV, dialysis dependent renal insufficiency, uncontrolled epilepsy) -known seropositivity for HIV -acute hepatitis B or C infection -chronic inflammatory bowel disease -prior malignant disease (exclusion: basalioma, non-metastasized solid tumor in constant remission diagnosed >3 years ago) -pregnancy or breastfeeding -active substance abuse or severely compromised compliance
Statistical Methods:	
Primary endpoint analysis:
 
The primary endpoint is the overall response rate (ORR) 6 months after end of treatment. It will be analysed by a one-sample non-inferiority binomial test. The one-sided significance level is 2.5%, the power is 80%.
 
It will be tested whether ORR will be non-inferior to 0.95, with non-inferiority margin (difference) 0.1, i.e. it will be tested whether the lower limit of the one-sided 97.5% confidence interval by Clopper-Pearson will be greater than 0.85.
 
Secondary endpoint analysis:
 
The pre-specified secondary endpoints will be analysed with appropriate statistical methods depending on the type of variable, e.g. rates are analysed by binomial test and exact 95%-confidence interval, time-to-event endpoints by one-sample log-rank test.

Number of Patients/ Sample size:	
To be assessed for eligibility: n = 88
 
To be assigned to the trial: n = 83
 
To be analyzed: n = 79

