9.2.2.1 Changes in Radiotherapy

Greater changes in the RT-regime define a dropout for the individual patient and are to be reported to the lead investigators or study management within 2 working days:

Dose reduction:	Reduction in total/daily dose of RT not indicated in the study (e.g. a reduction from 2 to 1.8 Gy would be possible, a change of dose of at most 10% is possible)
Dose increase:	Dose increase beyond the indicated RT dosage of the treatment (a change of dose of at most 10% is possible)
Discontinuation:	Pause of RT treatment for one or several days additional to regular pauses (weekend, public holidays) (a pause of RT for at most 4 working days is possible)
Dropout:	see 9.2.3.1

Holds and restarts of radiation treatment can be made at the discretion of the treating physician. Any changes in procedure of RT and reasons therefore need to be reported to the lead investigators.

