9.2.3 End of study

9.2.3.1 End of study for individual patients

There might be several conditions making it necessary for the patient to be taken out of the study:

- Excessive high grade toxicity (grade III or IV CTCAE)
- Withdrawal of informed consent for study participation of the patient (in that case, the patient is excluded)
- Treating physician's decision considering the general medical condition of the patient to end study
- Loss of contact to the patient
- Confirmed or suspected pregnancy
- Major violations of the study protocol (e.g. inability to adhere to the study schedule)
- Death of the patient

Each preliminary end of treatment has to be documented and patient is monitored concerning the remission status and overall survival as he/she is not included in the treatment analysis (per protocol).

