11.2 Proposed sample size/Power calculations

The primary endpoint ORR 6 months after the end of RT will be analyzed by a one-sample binomial test. Based on previous studies (Tsang 2003, Teckie 2015) the OR rate of the standard 30 Gy treatment is assumed to be 95%. The same OR rate is assumed for the interventional 20 Gy treatment. To show the non-inferiority of the interventional treatment to a non-inferiority margin of 10% (i.e. show that the ORR is greater than 85%) with 80% power and one-sided significance level 2.5% a number of 79 patients need to be analyzed. It is assumed that 95% of patients assessed for eligibility are assigned to the trial from which another 95% of patients can be analyzed (drop-out rate 5%). That is the needed number of patients to be assigned to the trial is 83 and the necessary number of patients assessed for eligibility is 88.

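### The 80% power belongs to the 79 patients left after drop-out, but the primary analysis is labelled ITT; an analysis of all 83 assigned patients does not have the stated power

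*Protocol*

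**What the plan says.** - **Sample size (Protocol 11.2).** The target is stated as "with 80% power and one-sided significance level 2.5% a number of 79 patients need to be analyzed". The step from assigned to analysed patients is "from which another 95% of patients can be analyzed (drop-out rate 5"%), which gives 83 assigned and 88 assessed for eligibility. The synopsis repeats 83 assigned and "To be analyzed: n = 79".
- **Test (synopsis).** The success rule is exact: "it will be tested whether the lower limit of the one-sided 97.5% confidence interval by Clopper-Pearson will be greater than 0.85".
- **Analysis set (11.3).** "The primary efficacy analysis will include all patients to be analyzed and will be performed according to the ITT principle". This is the only confirmatory analysis. Per-protocol analyses, without major violators, are listed separately as sensitivity analyses.
- **Drop-out and leaving the study.** Section 9.2.2.1 says "Greater changes in the RT-regime define a dropout for the individual patient". Section 9.2.3.1 lists reasons for leaving that include high-grade toxicity, loss of contact and death. It says of a patient whose treatment ends early: "patient is monitored concerning the remission status and overall survival as he/she is not included in the treatment analysis (per protocol").

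**The concern.** In 11.2 and the synopsis, the number to be analysed means the assigned patients minus 5%. In 11.3 the same words describe an ITT analysis, which would keep everyone assigned. The protocol therefore does not settle whether the denominator of the primary response rate is 79 or 83.

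The success rule allows only five non-responders, and about four patients are expected to fall between the two sets. How those four are treated can decide the result. For example, 74 responders out of 79 pass (lower limit 0.858), while the same 74 over all 83 fail (89.2%, lower limit 0.804). If the set is not fixed in advance, the denominator could be settled after the responses are known.

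**Working it through.** **Inputs.** Null value 0.85 (0.95 minus the margin of 0.10), assumed response rate 0.95, one-sided 2.5%, exact binomial test or equivalently the Clopper-Pearson limit, 79 analysed, 83 assigned, 5% drop-out. All come from 11.2, 11.3 and the synopsis. The response rate among drop-outs and the handling of a missing 6-month response are not given, so both are varied below.

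**Rule.** For each n, take the smallest r with P(X ≥ r | n, 0.85) ≤ 0.025. Power is P(X ≥ r | n, 0.95).

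**Step 1: the plan's own figure.** For n = 79, r = 74 (five non-responders allowed), size 1.56%, power 79.7%. The normal approximation gives (1.96·√(0.85·0.15) + 0.8416·√(0.95·0.05))² / 0.1² = 78.02, which rounds up to 79. The stated figure reproduces, for 79 patients who all have a response assessment.

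**Step 2: all 83 assigned, everyone assessed.** For n = 83, r = 78. Five non-responders are allowed, as at 79, because 77/83 has a tail probability of 2.60% under the null and just misses. Size is 1.02% and power 76.5%. Part of the fall from 79.7% is this discreteness of the exact test.

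**Step 3: all assigned, unassessed patients counted as non-responders.** With a fraction d unassessed, the response rate becomes 0.95 × (1 − d):

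| d | rate | power, n = 83 (r = 78) | power, n = 84 (r = 78) |
|---|---|---|---|
| 0% | 0.9500 | 76.5% | 87.3% |
| 1% | 0.9405 | 62.7% | 76.7% |
| 2% | 0.9310 | 48.6% | 64.0% |
| 3% | 0.9215 | 35.8% | 50.8% |
| 5% | 0.9025 | 16.9% | 27.8% |

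**Step 4: all 83, the four drop-outs have an observed response.** Let 79 patients respond at 0.95 and four at rate q. Power is 43.9%, 62.6%, 69.7% and 76.5% for q = 50%, 75%, 85% and 95%. It returns to 79.7% only if all four respond.

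**Step 5: error rate if only the 79 are analysed.** Set the rate over all assigned patients at exactly 0.85, with 5% dropping out and responding at rate q. The remaining patients then respond at (0.85 − 0.05q)/0.95, and the error rate is P(X ≥ 74 | 79, that rate):

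| q | rate in the 79 | error rate |
|---|---|---|
| 85% (unrelated to response) | 0.850 | 1.6% |
| 75% | 0.855 | 2.1% |
| 50% | 0.868 | 4.3% |
| 25% | 0.882 | 8.2% |
| 0% | 0.895 | 14.9% |

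The 2.5% level is crossed when the rate in the 79 exceeds 0.8584, that is at q = (0.85 − 0.95 × 0.8584)/0.05, about 69%. With exactly four of 83 lost instead of 5%, the last row becomes 13.9% and the crossing point about 68%.

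**Step 6: rounding.** 79/0.95 = 83.16, which rounds up to 84; 84/0.95 = 88.4, which rounds up to 89. The stated 83 yields 83 × 0.95 = 78.85.

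**The case against.** - **Drop-out may mean only a missing 6-month assessment.** Section 9.2.3.1 keeps patients who stop early under observation for remission status and excludes them only from the per-protocol analysis, which 11.3 treats separately. This stands. A reader might infer that patients with changed or stopped radiotherapy are removed from the primary analysis, but the documents do not say so. It narrows the group in question but does not resolve the set: 11.2 still bases its power on fewer patients than are assigned, and 9.2.2.1 uses the same word for altered treatment.
- **The missing-response rule may sit in a statistical analysis plan.** True, and its absence from the protocol is not the point here. No such rule can make both statements correct: if ITT means all 83, the power in 11.2 is for another set; if it means 79, the label is wrong.
- **An analysis of completers need not inflate the error rate.** This also stands. A reader might infer inflation as a matter of course, or take the 18.4% chance that 83 patients at a true rate of 0.85 yield at least 74 responders as the error rate. That figure assumes four non-responders are always removed. The protocol gives no response rate for drop-outs, and if drop-out is unrelated to response the size is 1.6%.
- **The power loss is partly discreteness and partly an assumed rule.** Correct. The 63% to 17% range applies only if unassessed patients count as non-responders.
- **The rounding is trivial.** Largely agreed; it is a minor correction.

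**Conclusion.** The point holds in this form: 11.2 and the synopsis on one side and 11.3 on the other describe different primary sets, and the stated 80% power belongs only to the 79.

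For all 83, power is 76.5% if everyone is assessed and responds at 95%. At the protocol's own 5% loss it is 17% if unassessed patients count as non-responders. Only if every drop-out is an observed responder does it return to 79.7%.

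If instead only the 79 are analysed, error control depends on how drop-outs respond. It is kept above roughly 69% response and lost below it: about 4% at 50%, and about 14% to 15% if none respond. A lower rate is plausible because death, toxicity and loss of contact are listed exit reasons, but the protocol does not establish it.

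It would also be wrong to infer that raising 83 to 84 repairs the power. Allowing a sixth non-responder gives 87.3% with no loss, but 76.7% at 1% loss and 27.8% at 5%.

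**What to change.** **Section 11.3 and synopsis.** Define the primary set as all assigned patients, with that number as the fixed denominator. State that patients with altered or stopped radiotherapy stay in with their observed 6-month response, in line with 9.2.3.1. Count death before the assessment, or a missing 6-month assessment, as non-response. Make the analysis of assessed patients a sensitivity analysis.

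**Section 11.2.** Restate the power for that set: 76.5% at 83 with no loss, and 63%, 49%, 36% and 17% at 1%, 2%, 3% and 5% unassessed. Use one term for patients without a response and another for the treatment changes in 9.2.2.1. Correct 83 and 88 to 84 and 89, and give the power of 84 with losses as well as without.

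**Cost.** Wording, one more patient if 84 is adopted, and a less favourable power statement. Restoring 80% at 5% loss under this rule would first be reached at 318 patients. For a rare disease the practical course is to report the lower power openly and keep missing 6-month assessments close to zero.

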12.1 Patient Identification List

All subject data will be collected in a pseudonymized form. Every trial participant can be identified by a unique subject identification code consisting the initial letter of the name of country, a three digit center code, a hyphen and three digit patient numbers. The identification code is assigned by the Study Center Muenster, Germany. A confidential subject identification list, which links the patients' names with the subject identification code, will be stored in the investigator site file locally at each participating site.

Patient numbers at one site are to be used by the radiation oncology and haemato-oncology departments simultaneously.

In case of study termination (either regularly or preliminary) patient name and patient number are kept.

12.2 Source Data

Source data are all information in original records and certified copies of original records of clinical findings, observations, or other activities in a clinical study necessary for the reconstruction and evaluation of the trial. Source data will be documented in various source documents (e.g. hospital records, doctor's report, subjects' diaries or evaluation checklists, x-rays) and then entered into the electronic Case Report Form (eCRF).

Data from patient self-documentation (i.e. EORTC QLQ C30 and STO22) are considered as source data and will be recorded on paper by the patient or a person assisting the patient and subsequently will be manually entered into the eCRFs by study site personnel.

12.3 Recording of Data /Case Report Form (CRF)

Data will be recorded electronically using an EDC (Electronic Data Capture) system. Only persons authorised to enter data into the eCRF will have access to the EDC system. All users will be trained to use the EDC system and will comply with the instructions in the study-specific user manual. They will have continuous access to the data and reports of subjects at their own study site. The investigator is responsible for ensuring that the study data will be documented correctly, completely and in a timely manner. A study team physician takes on responsibility for the collected data by signing electronically. The electronic signature according to FDA 21 CFR Part 11 is the legally binding equivalent of the study team physician's handwritten signature.

12.4 Data management

For data management, the validated data management system MACRO v4 (Elsevier InferMed) will be used. All entered data will be stored on servers of the University Hospital Muenster. The servers are located in a secure data center and behind a firewall in the network of the University Hospital Muenster. A backup of the data will be saved on a daily basis and all data changes will be recorded in an audit trail.

All data will be checked for plausibility during initial data entry. Missing or non-plausible data are highlighted by the system right at input at the clinical study site and may be corrected immediately.

[figure not shown]
After completion of data entry and data processing, the database will be locked and the data will be exported for statistical analysis. If required, the investigator will receive a CD-ROM of ISRT 20 Gy in localized indolent GI-NHL, Study protocol, version 01, 23.08.2020 Page 33 of 75

the eCRF data for archiving at the clinical study site. Study related documents must be archived for 10 years after the end of treatment.

13 Ethical and Regulatory Requirements

13.1 Ethical approval by institutional review board (University of Muenster)

Patientenschutz | Forschungsfreiheit

ETHIK 
KOMMISSION
der Ärztekammer Westfalen-Lippe und
der Westfälischen Wilhelms-Universität

Ethik-Kommission Münster · [name] · [name]

[name]
[name], Germany
[contact]
[contact]
E-Mail: [contact]
www.ethik-kommission.uni-muenster.de

Ethics Committee Muenster: **2019-023-f-S**, ethical approval July 15, 2019.

13.2 Declaration of Helsinki and Legal Requirements

The study will be conducted in compliance with the declaration of Helsinki (current version, October 2013, Fortaleza), the current legal provisions regarding data protection.

The present study can be launched for each participating study site as soon as a favorable opinion of the respective Ethics committee/IRB has been obtained.

In case of substantial amendments, new applications will be submitted to the relevant Ethics committee(s)/IRB(s).

No deviations from the protocol will be implemented without prior review and approval of the Ethics Committee/ IRB, except where it may be necessary to eliminate and immediate hazard to a patient enrolled on the protocol. In such cases, the deviation will be reported to the Ethics Committee/ IRB as soon as possible.

13.3 Patient Information and Informed Consent

Prior to inclusion into the study, the investigator informs each patient about nature, significance, implications, and risks of the study as well as about the patient's right to withdraw from study participation at any time without any resulting detriment. Patients are handed out the patient information sheet including the informed consent form which are provided for this study. Patient consent in study participation must be given in writing. Before informed consent is requested, patients are left sufficient time for consideration. They are provided the opportunity for clarification of any study issues.

The informed consent form is dated and signed by the patient and by the investigator. The originally signed informed consent form is archived in the investigator site file. A copy of the signed informed consent form (or a second original) is handed over to the patient together with a copy of the patient information sheet.

13.4 Data Protection

This study will be performed in compliance with the applicable data protection laws. Study personnel will handle all patient data in a strictly confidential way.

To prevent the identification of a person to whom study data belong, study data will be pseudonymized by means of the patient identification number (see chapters 6, 12.1). If patient documents (e.g., examination results) are transferred to an institution outside the study site, copies will be used on which the patient's name and initials are obscured and the patient identification number is indicated.

13.5 Financing

An application for funding was submitted to the IZKF Muenster and to the DLH-foundation.

14 Reporting and Publication Policy

14.1 Final report

After completion of the biometric evaluation, the lead investigators prepare a study report. The report includes all trial results, irrespective of whether favorable or not. It is signed by them and the person who is responsible for the evaluation.

Within 12 months after the end of the study, the lead investigators submit a summary of the final report to the Ethics committee/ IRB.

16.5 Appendix E (p. 44-62): Adverse Reactions (AR) CTCAE criteria version 3.0 (2006)

Grades

Grade refers to the severity of the AE (adverse event). The CTCAE displays Grades 1 through 5 with unique clinical descriptions of severity for each AE based on this general guideline:

- Grade 1** Mild; asymptomatic or mild symptoms; clinical or diagnostic observations only; intervention not indicated.
- Grade 2** Moderate; minimal, local or noninvasive intervention indicated; limiting age-appropriate instrumental ADL*.
- Grade 3** Severe or medically significant but not immediately life-threatening; hospitalization or prolongation of hospitalization indicated; disabling; limiting self care ADL**.
- Grade 4** Life-threatening consequences; urgent intervention indicated.
- Grade 5** Death related to AE.

Adverse Reactions (AE) criteria CTCAE version 3.0 (2006) for

BLOOD/BONE MARROW, CONSTITUTIONAL SYMPTOMS, DEATH, DERMATOLOGY/SKIN, ENDOCRINE, GASTROINTESTINAL, HEMORRHAGE/BLEEDING, HEPATOBILIARY/PANCREAS, METABOLIC/LABORATORY, PAIN-SELECT, PULMONARY/UPPER RESPIRATORY, RENAL/GENITOURINARY

16.6 Appendix F (p.63-74): Adverse Reactions (AR) LENT SOMA criteria

for ESOPHAGUS, STOMACH, SMALL INTESTINE/COLON, LUNG, URETER, KIDNEY, LIVER, BONE MARROW, SKIN/SUBCUTANEOUS TISSUE (Archambeau 1995, Cassady 1995, Coia et al. 1995, LENT SOMA for all anatomic sites 1995)

16.7 Appendix G: Standard Operating Procedure (SOP) Blood samples for research program

Standard_Blood samples for Gastric and Duodenal Lymphoma Research Programm_STTH

(within ILROG-Study ISRT 20 Gy in Localized Indolent Gastric or Duodenal Lymphoma)

Aims and scope:

This SOP aims at maintaining constant condition for the cytokine/biologic marker determination minimizing inter-observer variability and thus enabling high-quality data across all participating centers.

Therefore, the following standard applies to all study centers willing to participate in the “Additional Research Program” (see Study protocol 3.1.3 for further information).

Procedure:

Blood draws are intended at 6 consecutive dates (shown in Table 1) for analyzing the cytokines Interleukin (IL)-1 β , IL-4, IL-8 and TNFalpha as well as the proteins Syndecan1, MMP-2 and S100 proteins S100A8 and S100A9.

Visits	BV	IV-1	IV-2	IV-3	IV-4	FU-1	FU-2/3
	Baseline visit	First day of RT treatment	2nd day of RT (after 4 Gy)	5 th day of RT (after 10 Gy)	Last day of RT (after 20 Gy)	6 weeks after end of RT \pm 5 d	3 and 6 months after end of RT \pm 3 weeks
Blood draw	X		X	X	X		XX

Table 1.

Blood collection:

- collect 15 - **18 ml** of venous blood by sterile venipuncture using two 7.5 - 9 ml serum monovettes with clotting activator

-for clotting of blood, samples should be stored at room temperature for 20-30 minutes

- **Serum isolation and storage should be performed in a central/biology laboratory** of the clinic:

- the monovettes should be centrifuged for 10 min at 1500 x g

- the supernatant (serum) should be aliquoted by pipetting about 1ml of the serum into separate 2 ml cryotubes or 2ml Eppendorf reaction tubes, so that at least 4 serum aliquots are available from each blood withdrawal (attention: to avoid cellular contamination, release of half a centimeter of serum is indicated and pipette should not put deeper than half a centimeter over pellet into the monovette)

- Aliquots should immediately be stored **at least at -20°C in a freezer**

DANGER: - Repeated freeze-thaw cycles should be avoided and the time from blood collection to freezing of serum should not take longer than 40-60 minutes.

Transfer:

Each participating center stores its serum samples at maximum till the end of patient recruitment.

In the second half of the first year and after the end of recruitment, samples are sent on dry ice to the radiobiology lab in Muenster. Please make sure each sample is labeled with the participant's study ID and date of blood withdrawal. Only correctly labeled samples can be analyzed. Labeling of serum samples in accordance with the 6 visit dates 'baseline, 4 Gy, 10 Gy, 20 Gy, 3 months, 6 months':

'Country_center-patient-visit'

->e.g. 'G001-001-baseline' (G=Germany, 001=Muenster, 001=first patient, baseline visit).

For shipment, samples should be put in a fitting small box and placed in a bigger polystyrene box together with about 6kg dry ice. The box should be sealed with adhesive tape.

Please address your samples to:

[name]. [name]

Department of Radiation Oncology – Radiobiology Lab

University Hospital Münster

[name]

[name]

Germany

In case of questions concerning sample handling and transfer, please do not hesitate to contact us ([name]. [name]: [contact]. [contact] or Dr. [name]: [contact] [contact])

Material:

+ 7.5 - 9ml serum monovettes with clotting activator

+ pipette (e.g. Pasteur pipette)

+ 2ml cryotubes or 2ml Eppendorf reaction tubes

+ centrifuge

+ freezer

+ dry ice

+ small box

+ polystyrene box

